Auricular Percutaneous Electrical Nerve Field Stimulation (PENFS) using the BRIDGE device for Post-Operative Pain Control in Patients Undergoing Liver Transplantation

NCT03265249

Document Date: 09/24/2020

Purpose of the Study

Pain after liver transplantation is unavoidable but it often has significant consequences for patients during their recovery. Opioid medications are the cornerstone of all pain control plans post-liver transplantation; nonetheless, they come at a cost with multiple side effects and potential serious adverse effects. Opioids have a profound impact on postoperative gastrointestinal (GI) motility via activation of the μ-opioid receptors of the small and large intestines. Slowed gastrointestinal motility causes discomfort, pain, and nausea. In fact, opioid medications have been shown to increase the incidence of postoperative ileus which can result in delayed time to return of bowel function, longer hospital stays, increased incidence of complications, and decreased patient satisfaction. With the use of a novel Auricular Percutaneous Electrical Nerve Field Stimulation (PENFS): the BRIDGE device (manufactured by Key Electronics [Jeffersonville, IN, USA] and distributed by Innovative Health Solutions [Versailles, IN, USA]), pain perception in post-operative patients may be modulated. There is ample data on the efficacy of auricular acupuncture and various transcutaneous auricular neurostimulation devices for acute pain relief, including post-operative pain. However, the novelty of this device is in using alternating currents of stimulation over a large field and with higher voltage in order to influence central pain areas. This has the potential to reduce the use of opioid medications, which in turn will reduce the incidence of postoperative ileus and reduce patient need for and dependence on narcotic pain medications. This can have an enormous economic impact due to decreased length of hospital stays for patients who undergo liver transplantation. The aim of the current project is to investigate the effectiveness this new, FDA cleared device in reducing or preventing post liver transplantation opioid use with improved pain control. If effective, this alternative approach may revolutionize post-operative pain management and have a substantial impact on health care costs and morbidity. In addition, opioid reduction could potentially lessen the national crisis of opioid addiction. The BRIDGE device has recently been approved by the U.S. Food & Drug Administration for use in accupuncture.

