Auricular neurostimulation is a potential novel and non-invasive method of pain control following liver transplantation in a growing patient population with the probability of significant impact on economics and morbidity. We propose a pilot study to investigate the effects of auricular neurostimulation in patients receiving a liver transplantation. We will investigate the effects of auricular neurostimulation with this novel device and compare it to the current standard of care for pain management following liver transplantation.

The BRIDGE device is an FDA-approved (510(k)140530) and commercially available device manufactured by Key Electronics (Jeffersonville, IN, USA) and distributed by Innovative Health Solutions (Versailles, IN, USA). BRIDGE is an ambulatory, neurological device which consists of a battery powered, externally affixed generator with 4 wire leads attached to 3 electrode/needle arrays and one single point needle. The arrays are designed to produce a field effect similar to surgically implanted peripheral neurostimulators. One BRIDGE device per patient will be used in this study. The electrodes will be placed percutaneously in the external ear with the help of a transilluminator to visualize the neurovascular

bundles. The BRIDGE device has recently been approved by the U.S. Food & Drug Administration for use in accupuncture.

Design & Procedures

This is a prospective, randomized study to determine the efficacy of the BRIDGE device in reducing pain and opioid use in patients following liver transplantation. Subjects will be randomized in a 1:1 ration to one of the below groups:

Group 1: BRIDGE device will be placed by a physician prior to start of the surgery with standard of care pain control analgesia

Group 2: Subjects will receive the standard of care pain control analgesia

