The electrodes will be placed percutanesously in the external ear with the help of a transilluminator to visualize the neurovascular bundles. Three electrodes will be placed on the ventral and one on the dorsal aspect of the ear. The electrodes will be taped and secured behind the ear next to the generator itself which is secured to the skin with adhesive. The entire device may be covered by longer hair. Device placement training of all physicians, research personnel and advanced practice providers will be performed. After completing the baseline assessments above, the BRIDGE device will then be placed on the right ear prior to any premedication.

The BRIDGE Surgical kit consists of: (1) An alcohol swab, (2) prep and stay swab, (3) round fixation plasters, (4) fixation plasters to fasten the generator, (5) Steri-strip adhesive vial, (6) Sterile wire harness pack, (7) Generator, (8) Tweezers, (9) Surgical marker, (10) Transilluminator.

Bridge Placement Details:

The neurostimulator placement will be performed as directed and per training protocol instructions

Before neurostimulator placement, the subject should be advised that some discomfort is normal at first but should report if the discomfort persists or gets worse after a few minutes. The patients should be advised that they may feel a slight pulsing sensation and perhaps a warming sensation in the ear to which the electrodes are affixed. The pulsing and warming sensation may disappear after approximately 5 minutes. If the discomfort level increases, the offending electrode can be slightly repositioned until the patient's discomfort level decreases to an acceptable level. If there is continued discomfort in one specific electrode, it may be removed by cutting the lead.

The electrodes will be placed percutaneously in the external ear with the help of a transilluminator to visualize the neurovascular bundles. Three electrodes will be placed on the ventral and one on the dorsal aspect of the ear. The exact location of the implantation may vary slightly from person to person but is determined by both knowledge of auricular neuro-anatomy and visualization of the neurovascular bundles by transillumination. The electrodes will be taped and secured behind the ear next to the generator itself which is secured to the skin with adhesive. The placement of the devices is within standard of care by properly trained medical doctors and advance practice providers.

The device will then be activated.

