Device placement will take approximately 5 minutes. The patient will remain at rest for the next 5 minutes. Care will be taken not to interfere with standard pre-operative procedures. If the electrodes become dislodged a qualified practitioner will re-apply them.

Subject will then undergo surgery as per standard of care. The patient's anesthesiologist will be informed ahead of time of the device placement. Anesthesiologist and operative room staff will be instructed to avoid manipulating the device while moving the patient or during the procedure.

Patients will be advised not to manipulate the device or immerse the device in water as it is water resistant but not water proof. If showering or washing hair, they should place a dry wash cloth or plastic covering over the area to protect the device. If the electrodes become dislodged a qualified practitioner will re-apply them.

Intraoperative and Postoperative Protocol

In those randomized to have the BRIDGE device, neurostimulation will be delivered below sensation threshold continuously for 120 hours, the duration of the device battery. The anesthesiology team will be informed of participation in the study prior to BRIDGE application. It will be discussed that any use of regional anesthesia or NSAIDs are not permitted in this study. If the anesthesiologist believes the patient has contraindications to other methods of analgesia or anesthesia, or if it may be in the patient's best

interest to incorporate regional anesthetic techniques, the patient will be excluded from the study. Operating room staff will be instructed to avoid manipulating the device while moving the patient or during the procedure. The device does not interfere with any monitoring routinely used in the operating room.

All patients will undergo general anesthesia per standard of care. There will be no intraoperative or postoperative use of regional pain therapies (i.e. epidural anesthesia, tranversus abdominis plan blocks); anesthetic plan will otherwise be per treating physician. Once the procedure is over and the patient is extubated and transferred to the postoperative care unit, both groups (those with the device and those without) will continue to receive postoperative pain control per standard of care, as determined by the anesthesia and surgical teams. During the hospitalization, the postoperative pain control in all patients (both groups) will be per standard of care (opioids) per the adult liver transplant protocol.

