Localized discomfort if the electrodes should become dislodged during the wearing of the device - Rare (event rate 1% - < 5%)

Localized dermatitis - Rare (event rate 1% - < 5%)

Drop in blood pressure - Rare (event rate 1% - < 5%)

Syncope (fainting) - Rare (event rate 1% - < 5%)

Adverse effects to supporting personnel

Skin piercing with percutaneous needles - Rare (event rate 1 % - < 5%)

There are numerous, possible direct and long-term benefits to the subjects in this study. The results of this study may provide important insights to the medical field regarding a new, non-pharmacologic therapy that could improve pain control and quality of life for patients undergoing liver transplantation. If effective, a significant decrease or prevention in post-operative opioid use would be a major breakthrough in healthcare. This treatment would then have the potential to be extrapolated to other post-operative settings and populations.

Data Analysis & Statistical Considerations

This randomized study and the subjects will be randomized 1:1 ratio to the treatment groups. The primary efficacy endpoint is opioid usage after surgery in the two groups, and the related secondary endpoint is pain score in the two groups at the end of surgery. Normality possible transformations to attain normality of these variables will be assessed. These variables will be analyzed using either a two-sample t-test or non-parametric Wilcoxon test, depending on whether the outcomes are normal or non-normal. Analysis will be conducted under Intent-To-Treat (ITT), and any missing outcome will be imputed under missing at random (MAR) using multiple imputation methods. In addition, complete case analysis will be conducted. Continuous outcomes, adjusted for covarites, will be examined using regression analysis. Significance of the results will be examined at a two-tailed 0.05 alpha level.

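### The aim is less opioid with better pain control, but the plan tests opioid use alone in an unmasked trial and names no pain analysis over the same post-operative days.

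*Combined protocol and SAP*

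**What the plan says.** **Aim.** Purpose of the Study gives the aim as "reducing or preventing post liver transplantation opioid use with improved pain control". Design & Procedures calls the trial a "study to determine the efficacy of the BRIDGE device in reducing pain and opioid use".

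**Comparator and masking.** The control is standard care without an inactive device: "Group 2: Subjects will receive the standard of care pain control analgesia". The only blinding described is the envelope method of allocation. Under Study Interventions, "The patient's anesthesiologist will be informed ahead of time of the device placement". The device sits on the ear, is worn for 120 hours, and is hidden only in some patients: "The entire device may be covered by longer hair".

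**Who determines opioid use.** Under Intraoperative and Postoperative Protocol, both groups "will continue to receive postoperative pain control per standard of care, as determined by the anesthesia and surgical teams". The same section refers to the adult liver transplant protocol, whose rules are not given, and says that oral opioids are started as needed once the patient tolerates oral intake.

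**Analysis.** Data Analysis & Statistical Considerations states: "The primary efficacy endpoint is opioid usage after surgery in the two groups". It gives no unit or time window for opioid use. Its only entry for pain reads: "the related secondary endpoint is pain score in the two groups at the end of surgery". The list of other secondary outcomes contains no pain outcome.

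**Pain data.** Technical Details provides for a daily sheet on post-operative days 0-6 that includes pain intensity, the APS-POQ-R, and a 0-10 rating of average pain over the past week.

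**The concern.** Opioid use is a sound measure of analgesic benefit when pain is equal or lower. When pain is not examined over the same days, lower use has two readings: the device relieved pain and less opioid was needed, or less opioid was given or requested because a device was known to be in place. Knowledge of allocation can act through the teams who determine analgesia and through patients who take opioids as needed.

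The planned pain endpoint cannot separate these readings, because it is taken at the end of surgery, before post-operative opioid use has built up. At stake is whether a significant primary result can be read as support for the joint aim that the protocol states.

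**Working it through.** **1. Aim against analysis.**

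| Element | Aim | Planned analysis |
|---|---|---|
| Opioid use | Reduced | Primary; after surgery, no window |
| Pain | Improved | Secondary; one score at end of surgery |
| The two together | Less opioid with better pain control | None |

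The gap is in the analysis, because pain intensity is collected on post-operative days 0-6. The daily sheet suits this purpose better than the 0-10 rating, which asks about the past week and so reaches back beyond the early post-operative days.

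Patients who need regional techniques for additional pain control are excluded at that point. This may also take some poorly controlled patients out of view.

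**2. The plan's own power figures.** For a two-sample t-test with n per group, two-sided alpha 0.05 and effect d in SD units, the noncentrality is d × √(n/2) on 2n − 2 degrees of freedom. Solving for 80% power gives d = 0.809 at n = 25 (plan: 0.81) and d = 0.712 at n = 32 (plan: 0.71). Both reproduce, so the same method is used below.

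**3. What unmasked behaviour could do to the primary test.** Assume no true device effect, and opioid use lowered in the device group by b SD through prescribing or requests. The values of b are assumptions. The planned enrollment is 35 per group; 25 per group is the unfunded minimum.

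Example at n = 35, b = 0.3: noncentrality 0.3 × √17.5 = 1.255, critical value 1.995 on 68 df, rejection probability 23.6%.

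| b (SD, assumed) | 25 per group | 35 per group |
|---|---|---|
| 0 | 5.0% | 5.0% |
| 0.1 | 6.4% | 7.0% |
| 0.2 | 10.7% | 13.1% |
| 0.3 | 18.0% | 23.6% |
| 0.5 | 41.0% | 54.1% |

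These are conditional results. They show what follows if the shift occurs, not that it does.

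**4. Would a combined opioid-pain score solve it?** Each patient's ranks on opioid use and on pain are summed and the groups compared. Simulation: 35 per group, within-patient correlation 0.3 (assumed), 6,000 trials per setting, percentage significant in favour of the device.

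| Opioid shift | Pain shift | Meaning | Rank score | Opioid alone |
|---|---|---|---|---|
| −0.3 | +0.3 | Withholding, pain rises | 2.5% | 24% |
| −0.5 | +0.3 | Withholding, pain rises | 7% | 54% |
| −0.5 | 0 | Opioid bias only | 24% | 54% |
| −0.3 | −0.3 | Bias on both, no true effect | about 32% | about 23% |
| −0.5 | −0.5 | True benefit on both | 71% | 55% |

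The score guards against withholding that raises pain. It does worse than opioid use alone when unmasked patients also report less pain, and it cannot tell the fourth pattern from a true benefit.

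**5. Requiring both tests.** The chance that both are significant cannot exceed the smaller of the two separate chances. With a 0.3 SD bias on both it is therefore at most about 24%, against about 32% for the rank score. The price is power: with a true 0.5 SD benefit on each, it is at most 54%, and would be 0.541 × 0.541 = 29% if the outcomes were uncorrelated.

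**6. Precision of the pain comparison.** The 95% CI half-width is t × SD × √(2/n). At n = 35 with an assumed SD of 2 to 3 points on a 0-10 scale, it is 1.995 × 2 × 0.239 = 0.95 to 1.995 × 3 × 0.239 = 1.43 points.

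**The case against.** **The plan never says that lower opioid use alone proves efficacy.** This stands. A reader might infer that the plan would declare efficacy even if pain rose, but it states no success rule. Efficacy appears in the statement of purpose and in the label of the primary endpoint.

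**Clinicians do not set the endpoint alone.** This also stands. As-needed dosing gives patients a part, and a shared transplant protocol limits discretion to a degree that cannot be judged from the documents. That ward staff see the device is an inference; for the anesthesiologist, awareness is explicit. None of this supplies the missing comparison of pain over the same days.

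**It is a pilot against standard care, so lack of masking is accepted.** The background section does call it a pilot compared with current standard of care, and no sham is asked for here. The purpose is nevertheless worded as efficacy and tested at two-sided 0.05, so the wording and the supporting analysis matter.

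**The size of the bias is invented.** The 0.1 to 0.5 SD shifts are assumptions. The documents do not support a statement that the result will be biased, or by how much.

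**Pain is self-reported by unmasked patients.** This limits any remedy. A same-window pain analysis exposes withholding that raises pain, but does not remove expectation from the pain reports.

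**Conclusion.** The concern holds as a mismatch between a joint aim and a test of one half of it, in a trial where those who determine opioid use can know the allocation. Followed as written, the plan cannot distinguish opioid sparing from less opioid being given or requested.

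The possible size runs from negligible (7% positive at a 0.1 SD shift, 35 per group) to serious (54% at 0.5 SD), and the documents do not say where in that range the trial lies. The figures rest on a constant shift, no true effect and a t-test.

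Two stronger readings are not supported. The documents do not show that bias occurs. Nor would a combined opioid-pain score correct for unmasking, as the case with bias on both outcomes shows. The trial remains worth running; what needs support is the claim about both pain and opioid use.

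**What to change.** 1. **Data Analysis & Statistical Considerations.** Keep the primary test. State one window for opioid use. Replace or supplement the end-of-surgery pain endpoint with mean pain from the daily sheets over that same window, as first secondary endpoint, reported beside the opioid result with a 95% CI.
2. **Claim.** State that a reduction in both pain and opioid use will be claimed only if the opioid test is significant and the same-window pain difference is also significant in favour of the device. Otherwise report only lower opioid use under open-label care, with the pain CI.
3. **Design & Procedures and the analysis section.** Describe the comparison as adding an unmasked device to standard care, and state the open-label limitation.
4. **Optional.** If an integrated opioid-pain rank score is added, state that it guards only against withholding that raises pain and does not protect when pain reports are also biased.

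Before fixing the window, confirm which days the sheets cover. Technical Details gives post-operative days 0-6 but also visits 4 through 9, Experimental Design gives device days 1-5, and the visit table is not in the text available here.

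Cost: wording changes and one further analysis, with no new data collection if the sheets cover the window, and no sham. The downsides are a narrower claim if only opioid use falls, lower power for the joint claim, and reliance on self-reported pain that is itself unmasked.

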Patients currently or awaiting listing for a liver transplant will be prescreened by study personnel prior to their clinic. A member of the clinical care team known to the potential subject will introduce the study and/or study personnel once initial eligibility is confirmed. All patients eligible for liver

transplantation will be assessed for eligibility and potential study participation. All transplant patients undergo social and psychological evaluation prior to transplant. The clinical and study team will address any cognitive issues prior to transplant. Subjects that signed consent greater than 1 month prior to transplant will be contacted at the time of transplant notification to confirm continued desire to participate. Patients with liver failure may also experience liver encephalopathy that would impair their ability to consent. For subjects experiencing hepatic encephalopathy we will consent their legally authorized representative prior to transplantation. Subjects will be re-evaluated following the liver transplant procedure for consent appropriateness. We anticipate enrolling 35 participants in each group, for a total of 70 subjects. We will exclude pregnant females form this study as part of clinical standard of care for liver transplantation.

Inclusion criteria:

≥18 years of age but < 70 years of age

Actively listed for isolated liver transplantation

Subject or legally authorized representative able to sign informed consent

Not currently treated with opioids or any medications that may interact with opioids

English speaking

Willing and able to participate and consent to this study

Exclusion criteria:

Diagnosis of acute liver failure or primary sclerosing cholangitis (PSC)

Anticipated that the subject will require a new roux-en-y hepaticojejunostomy

Current use of opioid use or other substance abuse.

Chronic pain disorders

Need for regional anesthesia (regional nerve blocks or epidurals)

Adhesive allergy/sensitivity

Subject admitted to the ICU at the time of transplant

Pregnancy

Subjects who meet eligibility and sign the consent form will be eligible to be enrolled into the study at the time of transplant. All eligible subjects will be recruited from Duke Transplant clinics or during hospital admission prior to transplant.

Study Interventions

Technical Details

Subjects will prospectively complete the following questionnaires at different time points during the study (see Table 1 for timeline):

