Other secondary outcomes are: postoperative nausea and vomiting, postoperative ileus, postoperative immobility, length of hospital stay, incidence of ileus and time to return of bowel function, time to physical function, complications, and re-hospitalization. Continuous variables here will be analyzed using two-sample t-test or non-parametric Wilcoxon test, depending on whether the variables are normal or non-normal; categorical variables will be compared using chi-squared tests; time to event analysis will be examined using Kaplan-Meier curves. In addition, adjusted continuous outcomes will be examined using regression analysis; adjusted dichotomous outcomes will be examined using logistic regression; and adjusted time-to-event analysis will be examined using Cox proportional models. These analyses are exploratory, and significance will be assessed with and without adjusting for multiple testing.

Adverse events of this trial are infections and complications. Rates of infections and complications between the groups will be examined using Fisher's exact test or Chi-squared test.

Power: At the least (without any research funding) 25 subjects each will be randomized to the treatment groups. At alpha = 0.05 and 80% power and 25 subjects randomized to treatment groups, we should be able to observe effect size of about 0.81 between the two groups on the outcome of opioid usage; if we secure external funding, we should be able to randomize at least 32 subjects to each of the treatment groups. With 32 subjects in each groups, at alpha = 0.05 and 80% power, we should be able to observe effect size of 0.71 between the two groups. If we assume a 20% dropout rate, with the above sample sizes, we would observe effect sizes between .69 and 0.80 (Cohen, 1988).

Analysis will be conducted using statistical software SAS 9.4 (SAS Institute, Inc., Cary, NC).

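### The plan has no rule for death: as written, missing outcomes after a death are imputed as if the patient were alive, and recovery times would by default be censored at death

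*Combined protocol and SAP*

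**What the plan says.** All the analysis rules are in Data Analysis & Statistical Considerations.

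- **Primary endpoint.** Opioid usage after surgery, by t-test or Wilcoxon, under intention to treat. No time window or unit is given.
- **Missing data.** "any missing outcome will be imputed under missing at random (MAR) using multiple imputation methods". A complete case analysis is added. Neither sentence distinguishes a patient who died from one who withdrew or missed a form.
- **Secondary outcomes.** The list includes "length of hospital stay, incidence of ileus and time to return of bowel function, time to physical function, complications, and re-hospitalization". The plan calls these analyses exploratory.
- **Methods for the secondary outcomes.** The method follows from the type of variable alone: "Continuous variables here will be analyzed using two-sample t-test or non-parametric Wilcoxon test, depending on whether the variables are normal or non-normal". Chi-squared tests are named for categorical outcomes, and Kaplan-Meier curves and Cox models for time-to-event outcomes.
- **Adverse events.** Only infections and complications are named.

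Elsewhere, Intraoperative and Postoperative Protocol takes times to sitting and walking from patient surveys, ties discharge to the treating physician's criteria, and schedules a telephone call on day 30. Under Screen failures, a patient who cannot complete visit 2 is a screen failure with no follow-up assessments.

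No section names death, mortality or survival as an outcome, adverse event, censoring event, competing event or reason for missing data.

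**The concern.** An outcome that does not exist because the patient died is not a missing value. Imputing it under MAR assigns the patient the opioid use or pain score of a comparable survivor and hides the death. Censoring a recovery time at death makes the same assumption: that the patient would have recovered at the rate of those still under observation.

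For length of stay and re-hospitalization the gap is of another kind, because the plan is silent. One obvious coding, stay counted to the day of death and readmission set to no, turns an early death into one of the best values in the arm. Purpose of the Study presents less opioid use and shorter stay as the expected benefits, so these are the endpoints on which such an artefact would mislead.

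The comparator is standard care without a sham device. If the rule is left open, the choice could be made by people who know which arm the deaths are in.

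**Working it through.** **The plan's own figures.** The inputs are two-sided alpha 0.05 ("Significance of the results will be examined at a two-tailed 0.05 alpha level") and 80% power. Solving the two-sample t-test (noncentral t) for the detectable standardized difference gives 0.809 at 25 per arm and 0.711 at 32 per arm. The plan states 0.81 and 0.71, so both reproduce. This point does not change them. The 20% dropout assumption does not name death as a component.

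**Where a death can go under the text.** The same patient can follow four routes:

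1. taken as observed, with an opioid total or a stay that stops at death;
2. imputed under MAR as a survivor;
3. dropped from the complete case analysis;
4. if very early, classed as a screen failure because visit 2 was not completed.

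These give different results, and none records death as a bad outcome.

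**How likely are deaths?** The plan says "We anticipate enrolling 35 participants in each group, for a total of 70 subjects". Mortality to day 30 is not given, so I assume a range. Expected deaths = 70 × p. P(at least one) = 1 − (1 − p)^70. The last column is the probability that the arms differ by two or more deaths, from two independent binomials of size 35.

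| Assumed p | Expected deaths | P(at least one) | P(arms differ by ≥2) |
|---|---|---|---|
| 1% | 0.7 | 51% | 7% |
| 2% | 1.4 | 76% | 18% |
| 4% | 2.8 | 94% | 34% |
| 6% | 4.2 | 99% | 44% |

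**Length of stay, if counted to death.** Assume a lognormal stay with median 10 days and log-SD 0.5.

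- Mean = exp(ln 10 + 0.5²/2) = 11.33 days.
- SD = 11.33 × √(exp(0.25) − 1) = 6.04 days.
- Standard error of the difference at 35 per arm = 6.04 × √(2/35) = 1.44 days.
- Shift from two day-3 deaths in one arm = (2/35) × (11.33 − 3) = 0.48 day, or 0.48/1.44 = 0.33 standard error.

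In 20,000 simulated trials with no true effect, two such deaths in one arm raised the false-positive rate from 5% to about 6% for either test. One death left it at about 5%. With a simpler assumption (survivors average 10 days, death on day 2 to 5), each death lowers the arm mean by (10 − 5)/35 = 0.14 to (10 − 2)/35 = 0.23 day.

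**Re-hospitalization, if coded no.** With an assumed 30% rate among survivors, one death in 35 gives 0.30 × 34/35 = 29.1%.

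**Recovery times.** Suppose two of 35 die before walking and all 33 others walk. Censoring the deaths, one minus Kaplan-Meier reaches 100%. The proportion who actually walked is 33/35 = 94.3%.

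**Primary endpoint.** With no window, unit or SD in the plan, no bias in opioid use can be computed. Two deaths would be 2/35 = 5.7% of an arm's values.

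**The case against.** A reader might infer that the plan's rules score an in-hospital death as a short stay with no readmission, and impute opioid doses for days after death, so that deaths favour the arm where they occur. The documents do not support that. The sentence on continuous variables only chooses between two tests; it does not say when a stay ends. A patient who dies never meets discharge criteria, so stay could equally be treated as missing, then imputed or dropped. Post-death opioid days presuppose a window longer than survival, and no window is given. Under MAR imputation a death would not systematically look like low opioid use. That happens only if the total to death is taken as observed, and the two routes cannot both apply to one value.

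Other objections also have force. Acute liver failure, ICU admission at transplant and age 70 or over are excluded, which may lower mortality. Stay, bowel function, mobility and re-hospitalization are exploratory, in what the protocol calls a pilot study. The chance of at least one death overstates the problem, since bias in a comparison needs an imbalance. Deaths might be reported under complications, though the plan does not say so.

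All of this limits the size and the wording of the point. It does not supply a rule for death, and it leaves untouched the two methods that are stated: imputation of any missing outcome without exception, and Kaplan-Meier with no competing event.

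**Conclusion.** The point holds in limited form. The plan does not say how death is handled. Read literally, its MAR rule imputes values that are absent because the patient died, and its Kaplan-Meier analyses would by default censor deaths as if recovery were still possible. For length of stay and re-hospitalization the coding is undefined. It is not set in favour of the arm with more deaths; a favourable result follows only from one possible coding.

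The effect is probably small: about half a day of mean stay for two day-3 deaths in an arm of 35, a third of a standard error. This rests on an assumed distribution of stay and on those deaths occurring, since the documents give neither a mortality rate nor a stay figure. The consequence for the primary opioid endpoint cannot be sized from the documents. The change is worth making because it is cheap and removes a choice that could otherwise be made after the deaths are known.

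**What to change.** In Data Analysis & Statistical Considerations:

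- **Imputation.** Limit MAR multiple imputation to values missing in patients who were alive when the value was due. Do not impute after death.
- **Opioid use.** Repeat the primary comparison as a Wilcoxon test with deaths at the worst rank, as a sensitivity analysis.
- **Length of stay.** Analyse time to discharge alive, with in-hospital death at the worst rank or as a competing event. Choose one in advance.
- **Bowel function, sitting and walking.** Use cumulative incidence with death as a competing event.
- **Deaths.** Report them by arm, and show re-hospitalization alongside them. A single composite of death or re-hospitalization is debatable and need not be required, and nor is opioid dose per day alive.

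The cost is a few sentences and a few lines of SAS code, with no new data and no change to sample size or alpha. The drawback is that stay becomes a rank or discharge-alive measure, less direct than a mean difference in days.
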